**VISN19:** The VISN19 PII team has delivered three buprenorphine waiver trainings in primary care settings to expand the workforce of prescribers qualified to prescribe buprenorphine. As of May 2019, there are 59 prescribers in the VA Eastern Colorado Health Care System (ECHCS) with a buprenorphine waiver with 7 PCPs and 8 Internal Medicine residents completing waiver training during Phase 1. In the VA Salt Lake City Healthcare System, there are 78 prescribers with a buprenorphine waiver. They have met with VISN leadership on a quarterly basis during Phase 1 to discuss progress and barriers. In collaboration with the MAT-VA Initiative, they have led monthly webinars on OUD diagnosis and treatment for a national audience. They

have also engaged Veterans, completing 10 semi-structured interviews of Veterans with OUD at VA Salt Lake City to understand perspective on primary care-based OUD treatment.

**VISN22:** The VISN22 PII team conducted key stakeholder interviews among PCPs, nurses, pain providers, addiction psychiatrists, and Veterans and analyzed site-specific baseline data on process and outcome measures for our two VISN22 pilot sites. They led three waiver trainings for a total of 46 providers at 2 sites. They are developing multiple products to support expanded implementation: a PowerPoint presentation for PCPs on how to recognize and treat OUD; a coding “cheat sheet” for PCPs and psychiatrists to use in managing patients with OUD (including ICD-10 and CPT codes); a training pathway for X-waivered prescribers to increase confidence in prescribing buprenorphine.

**VISN23:** The VISN23 PII team developed an opioid management guide to promote changes in inpatient opioid prescribing practices and improve recognition and management of OUD. They developed an order set to facilitate use of non-pharmacologic pain treatment options available in the hospital. Based on a survey of nationally available resources and guides for MOUD, they drafted a VHA-specific toolkit for improving recognition and management of OUD in the inpatient setting. One hospitalist prescriber has obtained an X-waiver during Phase 1. Finally, they identified synergies with colleagues expanding MOUD to Emergency Department settings where shared implementation strategies will be beneficial.

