Effectiveness	Number of patients with OUD retained on MOUD at 90 days and 180 days during the implementation period (i.e. treatment retention) 	
 
▪ Hospitalizations and ED visits related to OUD post-implementation
 
▪ Opioid-related or other drug overdoses in patients with OUD post-implementation
 
▪ Opioid dose for patients on LTOT post-implementation
 
▪ Concomitant opioid-sedative prescriptions post-implementation
 

Adoption	Number of providers (and/or clinics) providing MOUD post-implementation, stratified by type of provider, clinical setting 	Number of VISTA x-waivered providers post-implementation 
Implementation	
 
▪ Facilitators and barriers to implementation
 
▪ Fidelity, as measured by frequency and duration of Implementation Facilitation strategies and other implementation strategies
 
▪ Cost of implementation
 
	Variation in facility-level use of implementation strategies over time
Maintenance	
 
▪ Summary of facilitators and barriers at implementation clinics 6 months post-implementation
 
▪ Elements of program maintained, including adaptations
 
▪ Number of VISTA x-waivered and prescribing providers 6-month period post-implementation
 
	Number of OUD patients receiving MOUD 12-24 months after implementation

**Data source:** CDW; Semi-structured interviews; REDCap facilitation tracking logs; REDCap survey of ERIC strategies.

drug overdoses. Coding strategies will be adapted as necessary to address Cerner adoption and CHOICE and MISSION use of community care records. **Adoption:** Outcomes focused on provider adoption of MOUD will be assessed. For each implementation site we will identify providers and assess the proportion of those providers who provide MOUD or who are credentialed to provide MOUD (VISTA X-waivered providers). Changes in these proportions between the pre- and post-implementation periods will be assessed as an indicator of implementation success.

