**D.4d3. Analytic approaches:** Our non-randomized evaluation design is necessary because randomization was not possible due to our partnership with VISN leadership and outreach efforts for individual site participation. A key goal is to demonstrate to VISN and facility leadership the value of implementation; therefore, we will estimate implementation outcomes for each of our individual sites and pool implementation sites as appropriate. This will allow us to provide descriptive quantitative information about individual implementation efforts to be combined with qualitative findings about implementation success. Although these analyses will allow for some comparison of effectiveness across individual team efforts, we do not propose formal direct comparisons of teams. There are several statistical limitations to the non-randomized evaluation design that we will address through pragmatic approaches. To account for secular trends in increased use of MOUD that may not be due to our implementation efforts, we will track other related implementation efforts such as initiation of additional SCOUTT efforts, and monitor national dashboards to generate a secular rate among non-intervention sites. We will use this secular rate and test to determine if CONDUIT activities increase use of MOUD above this rate, rather than a null hypothesis of 0. Because we are calculating outcomes for each of the individual sites, the risk of a spurious finding due to multiple testing is possible. We will use caution when interpreting any moderate p-values (e.g. 0.01 to 0.05) as significant. For ease in reporting to VISN and site leadership, we will utilize direct pre- and post-implementation period comparisons. Additional multivariate adjusted analysis using time-to-event semi-parametric methods will also be explored. These models will focus on initiation of MOUD treatment, and will allow for examining clinical and demographic characteristics, including time from initial OUD diagnosis.

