**D.5g. Implementation, clinical and cost outcomes analysis:** We will aggregate the personnel time and financial resource data collected to calculate the total cost of IF for each implementation effort. Using an "intent-to-treat" approach with person-years as the unit of analysis, we will calculate separate multilevel mixed models for each clinical/RE-AIM outcome and cost outcome. We will pool implementation efforts across clinical settings as appropriate (e.g. all primary care implementation efforts will be combined into a single analysis). Exposure to IF implementation-as-usual conditions will be based on timing and randomized as appropriate to each project, such as stepped-wedge designs. We will account for clustering of patients across multiple exposure periods, as well as nesting of patients within clinical settings. This approach will allow assignment of at-risk Veterans to different facilitation levels as well as control for secular trends in pre-post implementation efforts. At-risk Veterans who were initially exposed to implementation-as-usual condition will be censored relative to outcome assessment for that phase if they or their provider is exposed to IF. The model will include an indicator variable for implementation and clinic program status, and an interaction between time and this indicator variable to assess for the independent effect of implementation separate of secular trends. Longer term costs, such as 12-month medical care cost trajectories following exposure to potential referral to MOUD will be included as appropriate. Markov models based on the outcome of the point estimates from the clinical and economic outcome models will be developed to estimate confidence intervals of key measures such as cost per additional at-risk patient receiving MOUD.

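### The secular-rate comparison in D.4d3 covers only use of MOUD; Adoption and the leadership reports rest on uncontrolled pre-post change

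*Combined protocol and SAP*

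**What the plan says.** **Use of MOUD (D.4d3, Analytic approaches).** The plan recognizes a secular rise and will "monitor national dashboards to generate a secular rate among non-intervention sites". It then says: "We will use this secular rate and test to determine if CONDUIT activities increase use of MOUD above this rate". No other outcome is named in that test.

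**Adoption (D.4d2, Implementation/clinical outcomes).** For each implementation site the plan takes the proportion of providers who provide MOUD or are X-waivered. It then states: "Changes in these proportions between the pre- and post-implementation periods will be assessed as an indicator of implementation success". No outside comparator or secular rate is given. Table 5 lists the primary Adoption outcome as "Number of providers (and/or clinics) providing MOUD post-implementation, stratified by type of provider, clinical setting", with the X-waivered count as secondary. So the table has a post-implementation count and the text has a change in proportion.

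**Reports to VISN and site leadership (D.4d3).** For these, "we will utilize direct pre- and post-implementation period comparisons". The plan does not say whether the secular rate will appear beside them. The same section calls showing leadership the value of implementation a key goal.

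**Other relevant text.** D.4d1 foresees a comparison with VHA sites outside MOUD-related implementation work, based on harmonized definitions of at-risk Veterans. D.5g plans mixed models for each clinical/RE-AIM and cost outcome, "with person-years as the unit of analysis", with a time-by-implementation interaction meant to separate implementation from secular trends.

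**The concern.** The plan gives a sound reason for not testing MOUD use against zero change, and that reason applies at least as strongly to prescribers. D.4d2 itself says that providers were the focus of the SCOUTT intervention. A concurrent program that D.4d3 intends to track therefore acts directly on the Adoption measure. Yet Adoption is where D.4d2 and D.4d3 state no control.

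With each site as its own control and nothing else, growth that would have happened anyway and growth caused by facilitation are added together. If the sum is labelled implementation success and passed to leadership, a site that only kept pace with the rest of VHA can look like a success. Decisions on scale and spread could then rest on that figure.

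**Working it through.** **1. What the Adoption rule returns.** Let a site's provider proportion go from a0 to a1, and the proportion at comparable outside sites go from c0 to c1 over the same quarters.

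- Rule in D.4d2: a1 − a0.
- Secular-adjusted contrast, parallel to the treatment of MOUD use: (a1 − a0) − (c1 − c0).

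If facilitation does nothing and both proportions rise by g, the first gives g and the second gives 0. The bias is the background change itself.

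**2. Whether D.5g repairs this.** D.5g covers each RE-AIM outcome by name, and Adoption is one. But its unit is person-years, it nests patients within clinical settings, and it censors at-risk Veterans. A proportion of providers has no patient person-years. D.5g names neither a provider-level model nor a provider denominator. Its contrast is facilitation against implementation as usual by timing or randomization (D.4d3 says randomization was not possible), and it does not name outside facilities. It also leaves the direct comparison for leadership unchanged.

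**3. Size for Adoption.** Not computable. Table 1 gives waivered and prescribing providers for FY19 only. Table 6 does not help, because its sample sizes are at-risk Veterans.

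**4. Illustration from patients on MOUD (Table 1, Q2 FY18 to Q2 FY19).** This assumes that the VISN rows include the listed facilities. Rest = VISN total minus listed Phase 1 facilities.

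| VISN | Phase 1 facilities | Rest of VISN | Growth in rest | Expected gain at Phase 1 facilities |
|---|---|---|---|---|
| 1 | 511 to 552 | 1,606 to 1,664 | 58/1,606 = 3.61% | 511 × 0.0361 = 18.5 |
| 19 | 386 to 400 | 447 to 463 | 16/447 = 3.58% | 386 × 0.0358 = 13.8 |
| 22 | 493 to 603 | 1,061 to 1,098 | 37/1,061 = 3.49% | 493 × 0.0349 = 17.2 |
| 23 | 77 to 87 | 408 to 451 | 43/408 = 10.54% | 77 × 0.1054 = 8.1 |
| All | 1,467 to 1,642 (+175) | 3,522 to 3,676 (+154) | 154/3,522 = 4.37% | |

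- Pooled rate: 1,467 × 0.0437 = 64; 64/175 = 37%.
- VISN-specific rates: 18.5 + 13.8 + 17.2 + 8.1 = 57.6; 57.6/175 = 33%.

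These are counts, and denominators also moved: Manchester's count fell from 153 to 139 while its rate rose from 22% to 46%. With denominators back-calculated from the rounded percentages, the rate in the rest of the four VISNs rose from about 28.1% to 30.6%, or about 2.5 points.

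**5. What such growth does to a raw pre-post test of MOUD use.** Assumptions: baseline 24% (Table 2 national rate 23.7%), n independent patients in each period, two-sided alpha 0.05 (not stated in the plan), no clustering, no CONDUIT effect. Growth of 2 to 5 points is the range of VISN changes in Table 1, whose rows are taken to include the Phase 1 sites.

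P(significant rise) = Φ(g/SE − 1.96), with SE = √[(p0(1−p0) + p1(1−p1))/n].

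- n = 750, g = 0.02: SE = √[(0.1824 + 0.1924)/750] = 0.0224; Φ(0.895 − 1.96) = 0.14.
- n = 750, g = 0.05: SE = √[(0.1824 + 0.2059)/750] = 0.0228; Φ(2.197 − 1.96) = 0.59.
- n = 200: 0.07 and 0.20 for the same two values of g.

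The nominal value is 0.025. A test centred on a correct, known secular rate would stay near it.

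**The case against.** The strongest reply is that the plan already controls for secular trends well beyond MOUD use. D.5g promises it for every RE-AIM outcome, D.4d1 foresees non-participating sites, and D.4d3 will track related efforts. This stands in part: a reader might infer that no secular control exists outside MOUD use, and D.5g contradicts that. What remains is that D.5g is built on patients and does not say how a provider proportion would enter it, while D.4d2 does state a rule for Adoption, and that rule has no control.

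Three other inferences go too far.

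- **That national growth will be credited to CONDUIT as a matter of course.** For MOUD use the formal null is the secular rate. Adoption change is called an indicator, with no test stated, and site results are to be read with qualitative findings. The leadership text does not say the secular rate will be withheld. The misattribution is possible under the rules as written, not certain.
- **That opioid dose, opioid-sedative overlap and overdose share the fault.** These are patient-level outcomes, which D.5g's models cover on their face.
- **That all national training is independent background.** Section C.1 says of the VISN19 Phase 1 team that "they have led monthly webinars on OUD diagnosis and treatment for a national audience", and G.2 describes waiver trainings given nationally by a CONDUIT lead. Such work comes from CONDUIT's own teams. It may reach comparison sites and make an adjusted difference conservative.

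**Conclusion.** The concern holds for Adoption and for the leadership reports. In D.4d2 and D.4d3 the secular rate is applied only to use of MOUD. Adoption is judged by uncontrolled pre-post change, and D.5g does not clearly repair this because it describes no provider-level model. Background growth in prescribers can therefore be reported as CONDUIT's effect.

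The direction of bias is upward if prescriber proportions are rising outside CONDUIT, which the documents make plausible but do not measure. Its size for Adoption is unknown. The 33% to 37% must not be read as an Adoption figure, nor as an error in the MOUD-use test, which already has a secular control. It illustrates only how much of a raw one-year gain in patients on MOUD can match growth elsewhere in the same VISNs. The change should be made, but it does not undermine the planned test of MOUD use.

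**What to change.** 1. **D.4d2.** Define the Adoption effect as the site's pre-post change in the provider proportion minus the change in the same proportion, over the same calendar quarters, at sites not participating in MOUD-related implementation activities (the D.4d1 comparator). Use the same provider definition in both. Take the data from CDW, already the Adoption source in Table 5, or from the national dashboard behind Table 1, which reports waivered and prescribing providers by facility. Leave out the same three-month start-up period. Align Table 5 with the text on count or proportion.
2. **D.4d3.** Beside every pre-post figure given to leadership, show the concurrent outside change and the difference.
3. **D.5g.** Say whether it covers Adoption and, if so, give the provider-level model.
4. **Limits to state.** Trainings that CONDUIT teams deliver nationally may reach comparison sites and shrink the difference. Conversely, because this comparator excludes sites in other MOUD programs, the subtraction does not remove SCOUTT's effect at a CONDUIT site that also takes part in SCOUTT. Flag such sites from the tracking already planned.

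Cost: one additional provider-level extract, including provider denominators at outside sites (the harmonized definitions in D.4d1 concern Veterans), and extra columns in each report. Reported gains will probably be smaller.

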**D.4d. Quantitative evaluation:**

**D.4d1. Cohort identification:** To assess impact of IF efforts, we will identify a cohort of at-risk patients—those who have OUD but are not prescribed MOUD—to track their outcomes over time. Methods to identify at-risk patients will be harmonized across all implementation sites. These will include use of available data in the Corporate Data Warehouse (CDW), including medication/pharmacy records (inpatient and outpatient), toxicology screen results, primary care and mental health care utilization, inpatient admissions, comorbidity data, recent treatment and service use such as alternative pain treatments for the subgroup of MOUD patients with pain, and other information to determine at-risk Veterans appropriate for referral for MOUD. We will compare outcomes at each implementation site during the post-implementation period to outcomes prior to implementation, using each site as their own control. Each site will have a defined implementation start date and an implementation start-up period of 3-months in which outcomes will not be attributed to either the pre- or post-implementation period. For sites that have booster or additional implementation efforts, additional start dates of those efforts will be tracked. Harmonization of definitions for at-risk Veterans will also facilitate comparing sites across VHA not participating in MOUD-related implementation activities to examine secular trends and to rapidly identify targets for expanding the implementation efforts for MOUD referral in additional VISNs. A person-years approach will be used as Veterans may be at-risk and eligible for referral for MOUD at multiple time points during the three-year project.

**D.4d2. Implementation/clinical outcomes:** The Quantitative/Economic Core will work with the Implementation Core on two primary areas: (1) ensuring accuracy and consistency of assessments of RE-AIM

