outcomes across CONDUIT, with the Quantitative/Economic Core focused on Reach, Effectiveness, and Adoption; and (2) assisting in tracking and assessing frequency and duration of IF activities (e.g., logs of time related to implementation efforts that includes phone calls, meetings, education) across EF teams so that costs can be assigned to implementation efforts (**Table 5**). **Reach**: The primary reach outcome is the use of MOUD among at-risk individuals. At each implementation site we will identify at-risk individuals during the pre- and post-implementation periods, using modified criteria from the MOUD dashboard. Using the cohort definitions described above, each at-risk Veteran will be assigned an index date and at-risk person-years will be determined for both pre- and post-implementation periods as appropriate. The outcome will be calculated based on filling a qualifying prescription for buprenorphine or naltrexone. We note that this outcome is similar to the SCOUTT evaluation, however, the SCOUTT evaluation focuses on individual provider prescribing practices because providers were the focus of the intervention. In CONDUIT, any fill of buprenorphine or naltrexone will be counted because the focus on the implementation efforts are on the entire site, not individual provider practices. **Effectiveness**: Our primary effectiveness outcome will be the number of at-risk Veterans who participate in a full course of MOUD. This analysis will be similar to the Reach analysis, but will focus on the date of completing a full course of MOUD. Secondary outcomes will include rates of hospitalizations and ED visits related to OUD/SUD for Veterans who utilized MOUD compared to Veterans who do not use MOUD during the pre- and post-implementation period. Using a person-years approach we will identify at-risk individuals and determine the relevant time that they are at risk of potential adverse events. Hospitalization and ED visits with a primary or secondary diagnosis code of OUD/SUD will be identified using established methods, and will be guided by SCOUTT evaluation. We also propose examining the effect of implementation on a) total opioid doses; b) receipt of overlapping opioid-sedative prescriptions, and c) opioid-related or other

**Table 5.** Outcomes Mapped to RE-AIM Constructs

RE-AIM Construct	Primary Outcome(s)	Secondary Outcomes
Reach	Number of patients with OUD initiating MOUD during the implementation period in implementation sites 	

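### The secular rate for the MOUD-use test is to come from national dashboards and is not tied to the definition of the Reach outcome

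*Combined protocol and SAP*

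**What the plan says.** Section D.4d3 explains that sites could not be randomised and that MOUD use may be rising for other reasons. Its remedy is to "monitor national dashboards to generate a secular rate among non-intervention sites". It continues: "We will use this secular rate and test to determine if CONDUIT activities increase use of MOUD above this rate", in place of a null of zero. Results for leadership will be direct pre/post comparisons, with each site compared "using each site as their own control" (D.4d1).

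Reach is defined in D.4d1 and D.4d2. The at-risk cohort is "those who have OUD but are not prescribed MOUD", identified "using modified criteria from the MOUD dashboard". After an index date is assigned, "at-risk person-years will be determined for both pre- and post-implementation periods as appropriate". For the numerator, "The outcome will be calculated based on filling a qualifying prescription for buprenorphine or naltrexone". Table 5 words Reach as the number of patients initiating MOUD and lists 90- and 180-day retention separately, under Effectiveness.

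The dashboard figures in the document are the quarterly 'MOUD rate' columns of Table 1 (Buprenorphine Dashboard) and Table 2 (Opioid Use Disorder Dashboard). Neither table defines its numerator or denominator. The caption of Figure 2 describes a proportion of Veterans with OUD who receive MOUD.

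Two other places bear on secular trend. D.4d1 says: "Harmonization of definitions for at-risk Veterans will also facilitate comparing sites across VHA not participating in MOUD-related implementation activities to examine secular trends". D.5g plans person-year mixed models for each RE-AIM outcome, with a time-by-implementation interaction meant to separate the effect from background trend.

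**The concern.** In a non-randomised pre/post evaluation that expects growth in MOUD use, the credibility of a Reach claim depends on how that growth is removed. The null for the D.4d3 test should therefore be measured in the same way as the outcome.

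Reach is a flow: new fills per unit of time among people not on treatment. The share of people with OUD who are on MOUD is a stock. It rises if more people start, if those who start stay longer, or if fewer people are counted as having OUD. Only the first is Reach. Subtracting one year's share from the next does not remove the other two. If a share of this kind is used, a site could pass or miss the test because of retention or coding trends at other sites and not because of facilitation. D.4d3 also states no sampling error or between-site variation for the secular rate.

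**Working it through.** **1. Table 6 and the type of test it fits.** Inputs: power 0.80 (stated); two-sided 5% level (assumed, as Table 6 gives none). For a test against a fixed value, detectable effect = (1.96 + 0.84)/√n = 2.80/√n.

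- n = 50, 75, 200, 750 gives 0.396, 0.324, 0.198, 0.102. Table 6 states 0.40, 0.32, 0.20, 0.10.
- A two-sample comparison with n per period, 2.80·√(2/n), gives 0.560, 0.458, 0.280, 0.145 and does not fit.

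Table 6 is therefore reproduced as a fixed-null (or paired) calculation with no allowance for error in the comparator.

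**2. From a share to an initiation rate.** Assume a steady state with share on MOUD p, initiation rate i per at-risk person-year and discontinuation rate d per treated person-year. Then p = i/(i + d), so i = d·p/(1 − p). The documents give no d, so values of 0.5, 1 and 2 are assumed.

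- p = 0.24: i = 0.316d. p = 0.26: i = 0.351d. The difference is 0.0356d.
- The same 2-point rise therefore equals 1.8, 3.6 or 7.1 extra initiations per 100 at-risk person-years at d = 0.5, 1 or 2.
- With i unchanged, the rise also occurs if mean time on MOUD (1/d) lengthens by 0.351/0.316 = 1.11, that is by 11%.

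**3. How the printed measure can behave.** Inputs: Table 1 counts and percentages for VISNs 1, 19, 22 and 23; implied denominator = count/percentage.

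- On MOUD: 2,117 + 833 + 1,554 + 485 = 4,989 in Q2 FY18; 2,216 + 863 + 1,701 + 538 = 5,318 in Q2 FY19 (+6.6%).
- Implied OUD denominator: 18,160, then 17,176 (−5.4%).
- Share: 27.47%, then 30.96% (+3.49 points). With the first-year denominator held, 5,318/18,160 = 29.28%, so 30.96 − 29.28 = 1.68 points (48% of the rise) come from the denominator. Rounding of the printed percentages allows 25% to 61%.
- Manchester went from 153 (22%) to 139 (46%). Without it the share goes from 27.69% to 30.69%, with 1.04 of 3.00 points (35%) from the denominator. The rounding bounds are then −5% to 53% and include zero.

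**4. Which dashboard matters.** For the same quarter, Q2 FY19, Tables 1 and 2 give different 'MOUD rates': VISN1 40% and 34.1%, VISN19 26% and 19.2%, VISN22 28% and 22.4%, VISN23 24% and 20.6%.

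**5. Illustrative effect on a pre/post test.** Assumptions: rate p = 0.24 (near the national 23.7% in Table 2), n independent patients per period, no true effect, and a fixed secular change that is wrong by 0.5, 1 or 2 points. SE = √(2p(1 − p)/n), which is 0.0427 at n = 200 and 0.0221 at n = 750. The chance of an upper-tail rejection is 1 − Φ(1.96 − offset/SE).

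- Null too low, n = 200: 3.3%, 4.2%, 6.8%, instead of 2.5%.
- Null too low, n = 750: 4.2%, 6.6%, 14.6%.
- Null too high, power that should be 80%: 76.6%, 72.8%, 64.6% (n = 200); 73.1%, 65.1%, 47.4% (n = 750).

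**The case against.** The strongest reply is that the mismatch is inferred. Tables 1 and 2 say only 'MOUD rate', the Figure 2 caption names no dashboard, and D.4d3 does not say that these figures will supply the null. Dashboards may hold other measures, and D.4d2 itself takes its at-risk criteria from one of them in modified form. This stands: the documents show an unspecified link, not a proven error.

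Second, the plan already contains better tools. The harmonised definitions in D.4d1 may well be meant as the same comparator. The D.5g models cover each RE-AIM outcome, so Reach would also be adjusted for trend on its own scale. This stands in part. D.4d1 says only that harmonisation will make such comparisons easier, D.4d3 still names dashboards as the source, and D.5g does not say that non-participating sites enter the model.

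Third, the offsets and discontinuation rates above come from no part of the plan, and the Table 1 sites are Phase 1 implementation networks. This also stands, so none of these numbers estimates the bias at comparison sites.

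A reader might go further and infer that a dashboard level near 24% would itself be the null, which would give much larger error rates. The text does not support that: the rate replaces a null of zero, and the comparisons are pre/post, so a change is the natural reading. Nor do the documents support a drug-list mismatch. The dashboards' list is not given, and D.1 limits the project's MOUD to buprenorphine and injectable naltrexone.

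**Conclusion.** The concern holds in limited form. D.4d3 takes the null for its MOUD-use test from national dashboards without naming the measure, linking it to the Reach definition or allowing for its uncertainty. If a share on treatment is used, even as a change, the null can be wrong in either direction by an amount the documents do not fix.

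The size can only be illustrated. With a 24% rate and a null 0.5 to 2 points too low, both assumed, the false-positive chance is 3-7% at n = 200 or 4-15% at n = 750, against 2.5%. Table 1 shows that a dashboard share can move with its denominator, but the evidence is weak once Manchester is left out.

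It would be too strong to conclude that the Reach result is invalid or rests on this test alone, because D.5g plans a separate adjustment for trend. The gap should be closed before analysis.

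**What to change.** In D.4d3, state that the secular change will be computed from the Corporate Data Warehouse at non-participating sites, using the same at-risk definition, index-date rule, drug list, 3-month start-up gap and calendar windows as Reach. Carry its sampling error and between-site variation into the test, for example by adding those sites to the D.5g mixed model. Report this contrast beside the pre/post figures given to leadership, and keep the dashboards for monitoring.

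The cost is analyst time, a few sentences of text and wider intervals. D.4d1 already foresees the harmonised definitions. Table 6 should carry a note that it assumes a fixed comparator. For the controlled contrast at n = 200, with independent samples and before clustering, the detectable effect is 2.80·√(2/200) = 0.28 with a very large control group and 2.80·√(4/200) = 0.40 with four equal cells. Patients who contribute to both periods would narrow this and clustering would widen it. Small sites would depend more on pooling.
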